3 STUDY DESIGN

3.1 Overall study design

Study ALX0171-C203 is a randomized, double-blind, multicenter, multiple-dose study of ALX-0171 versus placebo along with standard of care in Japanese infants and young children aged 28 days to < 2 years hospitalized for RSV LRTI. A schematic of the study design is presented in Figure 1.

The overall study duration was expected to be approximately 12 months, with the planned study duration for each subject approximately 28 days.

The following dose levels were planned to be evaluated in four consecutive cohorts:

- Dose 1: target dose of 1.5 mg/kg
- Dose 2: target dose of 3.0 mg/kg
- Dose 3: target dose of 6.0 mg/kg

- Dose 4: target dose of 9.0 mg/kg

[figure not shown]
Each cohort was planned to consist of 15 subjects enrolled and randomly assigned to receive ALX-0171 or placebo, in an allocation ratio of 4:1 (N=12 active versus N=3 placebo per cohort). Study drug was planned to be administered once daily for 3 consecutive days and given along with standard of care treatment, which was determined by the Investigator according to institutional practice (taking into account the prohibited medications listed in CSP section 3.3.7.2).

In addition to the individual discontinuation criteria (see CSP section 3.4.2), criteria for stopping or pausing recruitment in each cohort and criteria to stop dose escalation were applied (see CSP section 3.1.1).

However, due to early termination of the trial, no subjects are screened for cohort 3 and cohort 4. Only 1 subject was screened for the second cohort but that subject was a screen failure. Enrollement was complete in Cohort 1 for which 16 subjects were screened and 15 of them were randomized into the treatment group ALX0171 1.5 mg/kg and placebo.

Therefore, the treatment groups ALX0171 3.0 mg/kg , ALX0171 6 mg/kg and ALX0171 9 mg/kg will contain no data and hence should not be reported in the respective outputs.

[figure not shown]
Figure 1: ALX0171-C203 – Study Design

IDMC=Independent Data Monitoring Committee

An overview of the study flow is shown in Figure 2.

Figure 2: ALX0171-C203 - Study Flow

*Or withdrawal visit at earlier time point in case of withdrawal

**Hospital discharge is allowed from Day 3 once all post-dose assessments have been completed.

3.2 Sample size

The planned sample size of 60 randomized and treated subjects was selected to provide information on the safety and tolerability of the different doses of ALX-0171 in Japanese infants and young children hospitalized for RSV LRTI. The sample size also allows for sufficient precision on the model estimated PK parameters, as described by Wang et al. [1] and it is expected to be informative on antiviral and clinical activity of ALX-0171.

However, due to early termination of the study, the enrollment could not be completed as planned. At the time of early termination, 17 subjects were screened and 15 randomized. All the analyses mentioned in the later sections of this document will be performed using data from these subjects.

3.3 Outcome measures to be considered for the abbreviated CSR

3.3.1 Safety Outcome Measures

- Treatment-emergent adverse events (TEAEs), as noted by healthcare staff and/or reported by parents/caregivers.
- Heart rate, respiratory rate (measured over a 1-minute interval) and SpO₂
- Body temperature and body weight
- Physical examination including the skin, ears/nose/throat, heart auscultation, lung auscultation, and abdomen
- Safety lab assessments: planned two times during the study (at screening and at the follow-up (FU) visit) and will be performed by the local laboratory in order to allow timely availability of the results. The following clinical laboratory test results will be evaluated:
 - Clinical chemistry: alanine aminotransferase, aspartate aminotransferase, creatinine, sodium, potassium, chloride, C-reactive protein, γ -glutamyltransferase, blood urea nitrogen
 - Hematology: hemoglobin, hematocrit, red blood cell count and indices, mean corpuscular hemoglobin, mean corpuscular hemoglobin concentration, platelet count (or estimate), white blood cell count including differential (lymphocytes, neutrophils, monocytes, basophils, eosinophils).

3.3.2 Clinical Activity Outcome Measures

- Heart rate, respiratory rate (measured over a 1-minute interval) and SpO2
- Wheezing as assessed during lung auscultation
- Cough during the night and during the day
- Respiratory muscle retractions (supraclavicular, intercostal, and subcostal).
- Body temperature and body weight
- Occurrence of apnea episodes.

3.3.3 Medical Interventions Outcome Measures

- Length of hospital stay for RSV infection
- Level, method, and duration of supplemental oxygen therapy
- Initiation of invasive or non-invasive ventilation (e.g., continuous positive airway pressure [cPAP] or HFOT)
- Level, method and duration of invasive or non-invasive ventilation
- Transfer to ICU and duration of stay in ICU.

3.3.4 Virology Outcome Measures

- Viral load, assessed in samples obtained via nasal swabs and quantified using plaque cultures (to evaluate replication-competent virus) and by RT-qPCR (to evaluate viral mRNA).

3.3.5 Pharmacokinetic Outcome Measures

- Systemic (serum) concentrations of ALX-0171 will be used as a surrogate for local (lung) concentrations.

3.3.6 Immunogenicity Outcome Measures

- Immunogenicity will be assessed by evaluation of anti-drug antibodies (ADA) in serum. Confirmed positive ADA samples will also be evaluated for their neutralizing potential.

4 GENERAL ASPECTS FOR STATISTICAL ANALYSIS

4.1 Analysis populations

The following populations will be considered for the analyses required for the abbreviated CSR:

- **All Screened Subjects Population:** All subjects with an informed consent form signed from the parent(s)/legal guardian(s) or legally acceptable representative(s), who were screened for eligibility.
- **Safety Population:** All subjects who received at least 1 administration of study drug, as treated (i.e., using the treatment that the subject actually received).

4.2 General Methods

All original and derived parameters as well as population characteristics will be listed and described using summary statistics. Frequency counts (number of subjects [n] and percentages) will be made for each qualitative variable. Descriptive statistics (n, mean, standard deviation [SD], median, minimum and maximum) will be calculated for each quantitative variable, and will only be presented if $n \geq 2$. If $n=1$, then only n and the mean will be displayed.

Repeated and unscheduled measurements will not be used for statistical analysis or summary tables, unless the repeated measurement was performed due to unreliable values/technical reasons, or the repeated measurement occurred prior to first study drug administration and is defined as the 'baseline'. The following rules will apply to any repeated measurements:

- If the repeated measurement occurs prior to the first study drug administration then the last obtained value of any repeated measurement will be used in the descriptive statistics.
- If the repeated measurement occurs after the first study drug administration then the original value of any repeated measurements will be used in the descriptive statistics.

All listings will include repeated and unscheduled measurements

All descriptive statistics will be presented by treatment group, and overall for disposition, demographic and baseline disease characteristics. The treatment groups were planned to be shown in the following order:

1. Placebo
2. Dose 1: target dose of 1.5 mg/kg

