4.6 Statistical Significance Level

No formal statistical testing will be performed. All confidence intervals (CIs) will be calculated at a 95% level of confidence.

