10 CONVENTIONS

10.1 Visit Windows

For post-baseline assessments, the CRF visit label will be used for the summaries. No windowing will be done.

For the full Schedule of Events refer to CSP, Version 3.0 (Page 24)

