10.2 Computation of Derived Data

The following calculations and derivations will be used:

- Change from baseline of parameter: (visit value of parameter – baseline value of parameter)
 - If either the baseline or post-baseline value is missing, the change from baseline is set to missing.
- Duration of AE (days) = (end date - start date +1)

- If either the end or start date is incomplete or missing, the duration of AE is set to missing.
- If AE ongoing at the end of the trial then AE duration = trial termination date – AE start date + 1. In the listing the duration will be presented as ‘>x days’ rather than ‘x days’.
- Hospitalization or ICU duration (days) = discharge date/time – admision date/time
 - If either the end or start time is missing, the duration is calculated using the date part only then; duration = discharge date – admission date +1.
 - If the subject is still hospitalized or in ICU at the end of the trial then the duration = trial termination date – admission date +1
- Time since onset RSV signs and symptoms (days) = date of ICF – start date of symptom + 1.
- AE onset day = AE start date - first study drug administration date + 1 (when AE start date \geq first study drug administration date
 - If AE start date < first study drug administration date then; AE onset day = AE start date - first study drug administration date
- Duration of oxygen supplementation (hours) is defined as total time of reported oxygen supply according to oxygen supplementation form.
 - If the time is missing or the date is incomplete then the duration is set to missing.

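### SAP 4.2 is inconsistent on repeated measurements, chiefly for a post-dose value repeated because the first reading was unreliable

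*SAP*

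**What the plan says.** SAP 4.2 (General Methods) handles repeats in two steps.

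The opening sentence bars repeated and unscheduled measurements from analyses and summary tables, with two exceptions. The first is worded "unless the repeated measurement was performed due to unreliable values/technical reasons" and is not tied to any period. The second covers a repeat taken before the first dose that serves as the baseline.

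Two bullets follow, introduced by "The following rules will apply to any repeated measurements". Before the first dose, the last value obtained goes into the descriptive statistics. After it, the rule is "If the repeated measurement occurs after the first study drug administration then the original value of any repeated measurements will be used". Neither bullet mentions the reason for the repeat.

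SAP 10.2 defines the derived variable as "Change from baseline of parameter: (visit value of parameter" minus its baseline value. SAP 10.1 adds: "For post-baseline assessments, the CRF visit label will be used for the summaries. No windowing will be done". SAP 4.6 states: "No formal statistical testing will be performed".

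**The concern.** The opening sentence selects by reason for the repeat and, in one exception, by timing. The bullets select by timing alone. Where the two criteria point to different values, the SAP gives two answers and no order of precedence.

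The case that matters is a measurement taken after dosing, found to be unreliable or technically faulty, and repeated for that reason. An analyst following the opening sentence would tabulate the repeat. One following the bullet would tabulate the faulty original. SAP 4.5 calls for double programming of the analysis datasets, so two programmers could each follow 4.2 and disagree, with no text to decide between them.

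At stake is the accuracy of the post-dose safety summaries (laboratory tests, vital signs, respiratory rate). In an abbreviated report on 15 randomized subjects these are a main part of the output.

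**Working it through.** **Step 1. Cross the two sets of rules by timing and reason for repeat (all from SAP 4.2).**

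| Timing | Reason for repeat | Opening sentence | Bullet | Agree? |
|---|---|---|---|---|
| Pre-dose | Unreliable or technical | Repeat admitted | Last value | Yes |
| Pre-dose | Other, repeat is the baseline | Repeat admitted | Last value | Yes |
| Pre-dose | Other, repeat is not the baseline | Repeat excluded | Last value | **No** |
| Post-dose | Other | Repeat excluded | Original | Yes |
| Post-dose | Unreliable or technical | Repeat admitted | Original | **No** |

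Two of the five cases conflict.

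**Step 2. Does the pre-dose conflict matter?** It needs a screening value repeated for a non-technical reason, followed by a later pre-dose value that becomes the baseline under SAP 4.3. The repeat would then bear only on a pre-baseline summary. The change-from-baseline shells (Tables 14.3.2.1, 14.3.3.1 and 14.3.4.1) begin at Baseline, so there is little or nothing for it to alter.

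**Step 3. Does other text settle the post-dose conflict?**
- SAP 4.3 defines baseline only.
- SAP 4.7 concerns imputation of missing data.
- SAP 6.5 brings unscheduled values into the worst-case laboratory shift table. It does not say which value enters the descriptive table.
- SAP 10.1 assigns values by visit label, which does not choose between two values under one label.
- SAP 10.2 uses the value at the visit without saying which value that is after a repeat.

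None of them resolves it.

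**Step 4. Is the case foreseeable?** Protocol 3.6.3.3 allows laboratory tests to be repeated when results are unexplained or unexpected. Protocol 3.6.3.7 anticipates abnormal results that turn out to be errors. SAP 6.5 schedules laboratory samples at screening and Follow-up only, so an erroneous Follow-up value would be that subject's only scheduled post-baseline entry for the test.

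**Step 5. Weight of one value.** The inputs are the planned 12 active and 3 placebo subjects per cohort (SAP 3.1). Let *d* be the error in the retained original and *n* the number of subjects with a value at that time point.

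- Shift in the group mean = *d*/*n*.
- Placebo, *n* = 3: *d*/3 = 0.333*d*.
- Active, *n* = 12: *d*/12 = 0.083*d*.
- Change from baseline is visit value minus baseline, so with the baseline fixed the mean change shifts by the same *d*/*n*, where *n* counts subjects with both values.

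The documents give no figure for *d* or for the number of such repeats, so no absolute size can be stated. With no such repeat the effect is zero.

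**The case against.** The strongest reply is that 4.2 has a sensible reading that gives effect to every sentence: the post-dose bullet is the default and the clause on unreliable values is its exception. If the bullet overrode that clause, timing alone would fix the value (last before dosing, original after) and the clause would do nothing. On this view the text is loosely drafted and does not direct anyone to use bad data.

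Much of that stands. A reader might infer that the SAP plainly orders unreliable values to be tabulated. The documents do not support so strong a claim, because the opening sentence points the other way. But the reconciling reading is not written down, and the words "The following rules will apply to any repeated measurements" count against it.

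A reader might also infer that the post-dose technical repeat is the only inconsistency. The table above shows that it is not, although the other one is of little consequence.

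Other replies limit the size. The placebo group is not there for formal comparison (Protocol 3.1.2). Investigators must ensure accurate case report form data (Protocol 9.2.1), and the data are to be clean at lock (Protocol 3.1.3). This makes an uncorrected known error less likely, but it does not choose between two values that are both properly recorded. For laboratory data, SAP 6.5 lists all results for any subject with an out-of-range or clinically significant result, and 4.2 adds "All listings will include repeated and unscheduled measurements". The listing helps a reader trace a value but does not change what the summary table shows.

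**Conclusion.** The inconsistency is real and minor. In the post-dose technical case SAP 4.2 gives two incompatible instructions, and the bullet applied literally would tabulate a value already judged unreliable. The pre-dose mismatch is a drafting fault with little or no effect.

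The consequence is confined to descriptive summaries, and no inference depends on it. The weights of 1/3 and 1/12 assume the planned 12:3 split with every subject contributing a value; the SAP reports 15 randomized but does not give the split actually achieved. Those weights show how sensitive small groups are to one value, not that an error occurred. Confidence is high that the wording conflicts. Whether it affects any number depends on how many such repeats there were, which the documents do not report and which may be none.

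**What to change.** Amend both bullets in SAP 4.2.

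1. Post-dose: keep the original value, except when the repeat was made because of a documented unreliable value or technical reason, in which case the valid repeat replaces the original. Identify these cases before unblinding, so that the choice is not made with treatment known.
2. Pre-dose: limit the use of the last value to a repeat that defines the baseline or was made for a technical reason, in line with the opening sentence.

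Deleting the exception from the opening sentence would also remove the post-dose conflict, but it would settle on the value judged unreliable, so the first route is better.

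The cost is one clause in each bullet, plus a blinded check of any post-dose repeats. No new data or analysis is needed.

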4.3 Baseline Definition

The Baseline value is defined as the value observed at the last timepoint before first study drug administration.

4.4 Rounding and decimal places

The following rules will be followed with regard to the number of decimal places and presentation of data in the tables and listings of safety data:

- All data will be listed according to the number of decimal places presented in the source data.
- Mean and median will be tabulated to one more decimal place than the source data.
- Minimum and maximum values will be tabulated to the same number of decimal places as the source data.
- Standard deviation (SD) will be tabulated to two more decimal places than the source data.
- A maximum of three decimal places will apply to all summary statistics.

4.5 Software and validation model

All statistical analyses will be performed using Statistical Analysis Software (SAS®) Version 9.3 or higher.

The following validation programming techniques, in agreement with PXL GDO EP SOPs, will be performed;

- Black box validation for ADaM datasets; double programming validation.
- White box validation for outputs; the reviewer has to execute the program step by step and to check and review the program as well as the datasets/log/output produced. The reviewer has also to verify the produced output and the data of the intermediate steps.

4.6 Statistical Significance Level

No formal statistical testing will be performed. All confidence intervals (CIs) will be calculated at a 95% level of confidence.

4.7 Missing Data

There will be no imputations of any missing data. All treated subjects will be included into the safety analyses as far as the data permit.

5 GENERAL CHARACTERISTICS

5.1 Subject Disposition

Subject disposition will be listed by subject and summarized (number and percentage of subjects) by treatment group and overall using all screened subjects. The tabulations will include the following information:

- Number of subjects randomized
- Number of subjects included in the safety population

Percentages will be based on the number of screened subjects.

In addition subject disposition will be summarized (number and percentage of subjects) by treatment group and overall using the safety population. The tabulations will include the following information:

- Number of subjects who completed the 3-day study treatment period
- Number of subjects who discontinued the study drug, with reasons for discontinuation
- Number of subjects who completed the trial
- Number of subjects who discontinued early from the trial, with reasons for termination

Percentages will be based on the number of subjects in the safety population.

Subject disposition by visit and by treatment group and overall will also be summarized (number and percentage of subjects) using the safety population.

5.2 Demographic and Baseline Characteristics

The following demographic and other baseline characteristics are recorded:

- Demographic characteristics:
 - Gestational ages (weeks)
 - Age (months)
 - Gender
 - Race
 - Asian specifications (if race is Asian)
 - Ethnicity
 - Body weight (kg) at baseline
 - Body weight (kg) categories at baseline:
 - 3.0 to < 4.0 kg
 - 4.0 to < 5.0 kg
 - 5.0 to < 7.0 kg
 - 7.0 to < 10.0 kg
 - 10.0 to < 12.0 kg
 - 12.0 to < 15.0 kg
 - Height (centimeters [cm])
 - Atopy history (yes/no/unknown)
 - Exposure to tobacco (yes/no)
 - Exposure to pets (yes/no)
 - Breastfed (yes/no)
- Baseline disease characteristics:
 - Heart rate (bpm)
 - Blood oxygen (SpO2) level (%)
 - Time since onset RSV signs and symptoms
 - RSV severity criteria:
 - Inadequate oral feeding (yes/no)
 - Inadequate oxygen saturation (yes/no)
 - Respiratory distress (yes/no)
 - Inadequate oral feeding (yes) and Inadequate oxygen saturation (yes) and Respiratory distress (yes)
 - Inadequate oral feeding (yes) and Inadequate oxygen saturation (yes)

Demographic and baseline characteristics will be listed by subject.

Demographic and baseline characteristics will also be summarized using descriptive statistics by treatment group and overall on the safety population.

5.3 Medical History

Medical history will be listed by subject, and will include at least the following: description of condition, body system, start date and end date (or ongoing, if applicable).

Medical history will also be summarized by treatment group and body system using the safety population.

5.4 Prior, Concomitant Medications and Oxygen Supplementation Therapies

Medications and/or oxygen supplementation therapies given on or after date of informed consent will be defined as concomitant medications. Medications and/or oxygen supplementation therapies that were given prior to date/time of informed consent, and which ended before date of informed consent will be classified as prior medications/ oxygen supplementation therapies.

If the start date is missing or unknown, the medication and/or oxygen supplementation therapy will be considered as concomitant (unless the end date is before the date/time of informed consent). If the end date is missing or unknown, the medication and/or oxygen supplementation therapy will be considered as concomitant.

When start and/or end dates of medications and/or oxygen supplementation therapies are only partially known, medications and/or oxygen supplementation therapies will be categorized using the following rules:

- If the partial end date is prior (<) to the date of informed consent (i.e., year or year & month is/are before the informed consent year or year & month) then the medication and/or oxygen supplementation therapy will be considered as prior.
- If the partial start date is equal or after (\geq) the date of informed consent (ie, year or year & month is/are after or the same as the informed consent year or year & month) then the medication and/or oxygen supplementation therapy will be considered as concomitant.

Summary tables will be provided for prior medications/oxygen supplementation therapies, and for concomitant medications/oxygen supplementation therapies by treatment group, by presenting the number and percentage of subjects taking each medication, classified using World Health Organization (WHO) Drug Dictionary (March 2017 (Enhanced)), anatomical therapeutic chemical (ATC level 4 class) class and preferred term. Multiple records of the same preferred term for the same subject and the same ATC level 4 class will be counted only once. A listing by subject will also be produced for prior and concomitant medications.

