6.1 Adverse Events

AEs will be coded by SOC and PT using the latest version of MedDRA available at the time of database lock. All adverse events recorded during the study will be listed with treatment emergent AEs flagged.

If an adverse event start date is missing or unknown, the adverse event will be considered as emergent (unless the adverse event end date is before the first dose of study drug).

When start and/or end dates of an adverse event are only partially known, adverse events will be categorized using the following rules:

- If the end time is missing and the end date is before (<) the first dose of study drug, then the adverse event will not be considered as emergent.
- If the partial end date is before (<) the first dose of study drug (i.e., year or year & month is/are before the first dose of study drug year or year & month), then the adverse event will not be considered as emergent.
- If the start time is missing and the start date is equal or after (≥) the first dose of study drug, then the adverse event will be considered as emergent.
- If the partial start date is equal or after (≥) the first dose of study drug (ie, year or year & month is/are after or the same as the first dose of study drug year or year & month), then the adverse event will be considered as emergent.

No imputation will be done of missing/partial date(time) fields. The dates and times will be presented in the listings as captured in the eCRF.

TEAEs or treatment-emergent SAEs are events temporally associated with the use of study drug (occurring during or after the first dose of study drug, or worsening in severity (for pre-existing conditions)), whether considered related to the study drug or not.

In the TEAE overview table, number and percentage of subjects for the following items will be provided:

- Subjects with at least one treatment-emergent adverse event (TEAE)
- Subjects with at least one serious TEAE
- Subjects with at least one TEAE leading to death
- Subjects with at least one severe TEAE as classified by the investigator
- Subjects with at least one TEAE for which the study drug was interrupted
- Subjects with at least one TEAE for which the study drug was discontinued
- Subjects with at least one TEAE that was considered treatment-related (relationship to study drug is related or possibly related or missing) by the investigator.

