15.2 Mock Listings

Listing 16.2.1.1: Subject Disposition (All screened subjects)

Subject Number/Site	Date of ICF	Randomization group	Date of Randomization	Randomization number	Treatment actually received*	Analysis population Safety
XXX/X		Placebo			Placebo	<YES>

All discrepancies between randomization and treatment group will be flagged.

Note to Programmer: Table sorted first by randomization group and then by subject ID.

Listing 16.2.1.2: Demographics (Safety Population)

Treatment Group: XXXXXX

Subject Number/ Site	Date of Randomiza- tion	Date of Gestational Age (weeks)	Age (month)	Gender	Ethnic Origin	Race	Asian	Height (cm)	Weight (kg)	Weight Category (kg)	Atopy History	Exposure to Tobacco	Exposure to Pets	Breast fed
XXX/X		XX	XX	MALE	HISPANIC OR LATINO	WHIT	E							
XXX/X		XX	XX	FEMALE	HISPANIC OR LATINO	ASIA	N	XXXXX						

Note to Programmer: Table sorted first by treatment group and then by subject number

Listing 16.2.1.3: Baseline Characteristics (Safety Population)

Treatment Group: XXXXXX

RSV Severity Criteria							
Subject Number/Site	Heart Rate (bpm) at Baseline	Blood Oxygen (SpO2) at Baseline	Time since onset	RSV Signs and Symptoms	Inadequate Oral Feeding (days)	Inadequate Oxygen Saturation	Inadequate Respiratory Distress

Note to Programmer: Table sorted first by treatment group and then by subject number

Listing 16.2.1.4: Medical History and Concomitant Diseases (Safety Population)

Treatment Group: XXXXXX

Subject Number/Site	Body System	Description of Disease/Procedure	Start Date DDMMYYYY	End Date DDMMYYYY	Ongoing at screening <YES>
<hr/>					

Note to Programmer: Table sorted first by treatment group and then by subject number

Listing 16.2.1.5: Prior and Concomitant Therapies (Safety Population)

Treatment Group: XXXXXX

Subject ID	ATC Level 4 Class verbatim	Prior/ Concomi- tant Preferred Term	First study drug administration Date/Time	Start Date/Time	End Date/Time	Ongoing at the end of trial?	Reason for use	Indication	Dose (unit)	Dosing frequency
				YYYY-MM-DD /HH:MM	YYYY-MM-DD /HH:MM	<YES>				

Prior medications are medications that were given prior to date/time of informed consent and which ended before date of informed consent
 Concomitant medications/oxygen supplementation therapies are medications/oxygen supplementation therapies which are ongoing at signing of informed consent or which started after the signing of informed consent

Listing 16.2.1.6: Exposure to Study Medication (Safety Population)

Treatment group : xxxx

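### SAP 5.4 classes a therapy as concomitant from its partial start date even when its known end date is before consent; SAP 6.1 has a parallel gap of little practical weight

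*SAP*

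**What the plan says.** **Therapies (SAP 5.4).** The section opens with two definitions: "Medications and/or oxygen supplementation therapies given on or after date of informed consent will be defined as concomitant medications", while those given earlier and "which ended before date of informed consent will be classified as prior medications/ oxygen supplementation therapies". The footnote to mock Listing 16.2.1.5 (SAP 15.2) repeats the second: "Prior medications are medications that were given prior to date/time of informed consent and which ended before date of informed consent".

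The date rules follow. A therapy with a missing start date is concomitant, "unless the end date is before the date/time of informed consent". For partly known dates there are two bullets, and the SAP says that these records are to be categorised by them:

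- The end-date bullet begins "If the partial end date is prior (<) to the date of informed consent" and returns prior. It is worded for partial end dates only.
- The start-date bullet returns concomitant when the "year or year & month is/are after or the same as the informed consent year or year & month". It does not mention the end date.

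No order of precedence is given.

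**Adverse events (SAP 6.1).** The structure is the same. With a missing start date, "the adverse event will be considered as emergent (unless the adverse event end date is before the first dose of study drug". With a partial start date, the event is emergent when the "year or year & month is/are after or the same as the first dose of study drug year or year & month", again without an end-date exception. Two further bullets return not emergent: one for a complete end date before first dose with the end time missing, the other for a partial end date before first dose. A fourth bullet makes an event emergent when its start time is missing and its start date is on or after the first-dose date; it has no end-date exception either.

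**The concern.** Classing doubtful dates as concomitant or emergent is a sound conservative convention. It should apply only while doubt remains. If the end date is known to fall before consent, the therapy is prior whatever the missing start day was. The SAP recognises this when nothing is known about the start and drops it when the month or year is known. More information therefore gives a less accurate class, which looks like an omitted clause rather than a choice.

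At stake is whether therapies stopped before study entry move from the prior table (14.1.2.4) to the concomitant table (14.1.2.5), under a listing footnote that says they do not belong there. For adverse events, an event over before dosing could in principle enter the TEAE tables.

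**Working it through.** The plan states no figure on this point, so the check applies the rules literally to test dates and compares the results with the SAP's own definitions. The dates are invented.

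**Therapies, consent on 20 February 2018**

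| Case | Start | End | Rule that applies | Result by rule | By definition |
|---|---|---|---|---|---|
| A | Feb 2018 | 12 Feb 2018 | partial start | concomitant | prior |
| B | 2018 | 10 Jan 2018 | partial start | concomitant | prior |
| C | 2018 | Jan 2018 | partial end and partial start | prior and concomitant | prior |
| D | Jan 2018 | 12 Feb 2018 | neither bullet | definition decides | prior |
| E | missing | 12 Feb 2018 | missing start, exception met | prior | prior |

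A and E differ only in that the start month is known in A. In A and B the partial-end bullet cannot help, because the end date is complete. C is a conflict without precedence.

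**Adverse events, first dose on 21 February 2018**

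| Case | Start | End | Rule that applies | Result by rule |
|---|---|---|---|---|
| F | Feb 2018 | 20 Feb, time known | partial start | emergent |
| G | Feb 2018 | 20 Feb, time missing | missing end time and partial start | not emergent and emergent |
| H | 2018 | Jan 2018 | partial end and partial start | not emergent and emergent |
| I | 21 Feb, time missing | 21 Feb, time known and before the dose | missing start time | emergent |

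All four ended before dosing, so none meets the SAP 6.1 definition of a TEAE. F and I are wrong outright; G and H are conflicts. H tests the logic only, since the collection window below rules it out in practice.

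**How many adverse events could be affected.** Protocol 4.1.2 collects events from signed consent. Protocol 3.6.1.1 requires randomization within 24 hours of arrival, and 3.3.4 requires the first dose within 3 hours of randomization. If consent follows arrival, the window between consent and first dose is at most 24 + 3 = 27 hours. An affected event must start and end inside that window and still have an incomplete start.

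**How often the therapy bullet would apply, on assumed dates.** Take consent on each of the 365 days of 2018, a true start 1 to 30 days earlier, and a complete end date anywhere from the start to the day before consent. That gives 365 × (1 + 2 + … + 30) = 365 × 465 = 169,725 combinations, all prior by definition.

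- Start known to the month: 56,354 / 169,725 = 33% are labelled concomitant.
- Start known to the year only: 160,270 / 169,725 = 94% are labelled concomitant.

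These shares apply only to records with a partial start and a complete end date before consent, and they depend on the assumed 30-day window. They do not estimate how many such records exist.

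**After the fix.** A, B and C become prior and F to I become not emergent. Records whose end date is missing, or not clearly before consent or first dose, stay concomitant or emergent.

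**The case against.** The best defence is that the SAP's intention is plain. The definition, the missing-start rule and the listing footnote all let a known earlier end date decide, so a careful programmer would do the same, and SAP 4.5 requires double programming of the ADaM datasets. This stands as to intent. It does not remove the fault: the SAP sends partly dated records to the bullets, and two programmers who both follow the bullet will agree on the wrong class.

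It is also fair that a wrong flag would be visible. Listing 16.2.1.5 prints start and end dates and Listing 16.2.1.1 prints the consent date. For adverse events with a missing end time or a partial end date, SAP 6.1 already has bullets returning not emergent, so the fault there is only the lack of precedence.

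Two stronger readings are tempting, and the documents do not support them.

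- A reader might infer that nearly every drug started shortly before admission with an unknown start day would be misclassified. That also requires a known end before consent; a drug continuing past consent is correctly concomitant. The 4-day limit in the inclusion criteria (Protocol 3.2.1) concerns symptom onset, not drug starts.
- A reader might infer that a mucolytic stopped before consent would be reported as prohibited use, since Protocol 3.3.7.2 permits mucolytics only until screening. But Protocol 3.3.7 records previous medications only if relevant for eligibility, no exclusion criterion in 3.2.2 names mucolytics, and the SAP's index of tables has no prohibited-medication table. Prohibited medication appears in mock Table 14.1.1.2 only as a reason for discontinuation.

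**Conclusion.** The concern holds for SAP 5.4. The partial-start bullet gives a class that contradicts the section's definition of prior therapy, its missing-start rule and the Listing 16.2.1.5 footnote. This is a rule that is wrong as written, not merely missing detail. SAP 6.1 has a parallel wording gap, with few or no events expected to fall into it.

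The consequence is small. The trial stopped early with 15 children randomized, SAP 4.6 plans no formal testing, and only descriptive prior/concomitant and TEAE outputs can change. With the planned split of 12 active and 3 placebo, one reclassified child moves a percentage by 1/12 = 8.3 or 1/3 = 33.3 points. That reflects the group sizes and says nothing about how often the rule errs. The number of affected records is not given and may be zero.

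The conclusion rests on reading the bullets literally, as the SAP instructs. It assumes nothing about the trial's actual dates.

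**What to change.** - SAP 5.4, partial-start bullet: add *except where the end date, complete or partial, precedes the consent date; such a therapy is prior*.
- SAP 6.1, partial-start and missing-start-time bullets: add *except where the event's end date/time precedes the first dose*.

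Alternatively, state once in each section that end-date rules take precedence over start-date rules, and that a complete end date counts as well as a partial one.

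The cost is a few words in each section and one condition in the dataset derivation. No new data are needed, and the conservative treatment of uncertain dates is unchanged.
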